10.10. Appendix 10: Study Conduct During a Natural Disaster

GUIDANCE ON STUDY CONDUCT DURING THE COVID-19 PANDEMIC

It is recognized that the Coronavirus Disease 2019 (COVID-19) pandemic may have an impact on the conduct of this clinical study due to, for example, self-isolation/quarantine by participants and study site personnel; travel restrictions/limited access to public places, including hospitals; study site personnel being reassigned to critical tasks.

In alignment with recent health authority guidance, the sponsor is providing options for study related participant management in the event of disruption to the conduct of the study. This guidance does not supersede any local or government requirements or the clinical judgement of the investigator to protect the health and well-being of participants and site staff. If, at any time, a participant's safety is considered to be at risk, study intervention will be discontinued, and study follow-up will be conducted.

Scheduled visits that cannot be conducted in person at the study site will be performed to the extent possible remotely/virtually or delayed until such time that on-site visits can be resumed. At each contact, participants will be interviewed to collect safety data. Key efficacy endpoint assessments should be performed if required and as feasible. Participants will also be questioned regarding general health status to fulfill any physical examination requirement.

Every effort should be made to adhere to protocol-specified assessments for participants on study intervention, including follow up. Modifications to protocol-required assessments may be permitted via COVID-19 Appendix after consultation with the participant, investigator, and the sponsor. Missed assessments/visits will be captured in the clinical trial management system for protocol deviations. Discontinuations of study interventions and withdrawal from the study should be documented with the prefix "COVID-19-related" in the CRF.

The sponsor will continue to monitor the conduct and progress of the clinical study, and any changes will be communicated to the sites and to the health authorities according to local guidance. If a participant has tested positive for COVID-19, the investigator should contact the sponsor's responsible medical officer to discuss plans for study intervention and follow-up. Modifications made to the study conduct as a result of the COVID-19 pandemic should be summarized in the clinical study report.

GUIDANCE SPECIFIC TO THIS PROTOCOL

The following emergency provisions are meant to ensure participant safety on study while site capabilities are compromised by COVID-19-related restrictions. Remote medical consultation and alternatives to study intervention dispensing, administration, and clinical laboratory assessments may allow continued study participation for participants in this trial. Before implementing any of these emergency provisions, the sponsor should be consulted to perform a benefit-risk analysis and to ensure the measures are executed and documented correctly.

As restrictions are lifted and the acute phase of the COVID-19 pandemic resolves, sites should revert to original protocol conduct as soon as feasible and in accordance with any country-specific regulatory requirements.

Screening and Randomization:

- Enrollment of new participants may continue based on the investigator's assessment of risks versus benefits, depending on the situation at a particular site, and the ability to monitor participant safety.
- Baseline visits for participants recently screened for this study should be postponed if the current situation does not allow for an orderly conduct of the study.

Dispensing/Administration of Study Intervention:

- For participants able to visit the study site, but who request to reduce visit frequency, or for whom limited access to the site is expected, an additional supply of oral study intervention, as well as PegIFN- α 2a where allowed per local regulations^a, can be provided.
- For participants unable to visit the study site, direct-to-patient (DTP) shipment or handover to a caregiver or delegate of oral study intervention may be implemented, where allowed per local regulations and if requested by the treating study physician. Where DTP shipments or handover to delegates are deemed necessary, the process must be coordinated between the site and sponsor staff following standard DTP procedures for arranging shipment and adhering to associated approvals and documentation requirements.
- JNJ-3989 should always be administered by a nurse at the study site or, if site visits are not possible, at the participant's home. Refer to Section 6.4, Study Intervention Compliance, in case a scheduled administration of study intervention (JNJ-3989, NA, or PegIFN- α 2a) is missed.

Continuation of Study Intervention:

- Any issue with continuation and/or provision of study intervention should be discussed with the sponsor and should be well documented.
- Study intervention should be continued if, in the assessment of the investigator, it does not result in risk to the participant. If at any time the participant's safety is considered at risk due

^a Providing additional PegIFN- α 2a to study participants is not applicable for sites in Japan, where weekly administration of PegIFN- α 2a must be performed at the study site by the investigator or his/her designee.

to study intervention, study intervention will be temporarily or permanently discontinued, while every effort should be made to maintain follow-up on study. The benefit of continuing study intervention should be assessed by the investigator for each individual participant, considering the potential impact of reduced direct clinical supervision on participant safety.

- If a participant develops a SARS-CoV-2 infection, the investigator should contact the sponsor to discuss plans for study intervention and follow-up. A decision to continue study intervention should be made by the investigator depending on symptoms and concomitant medication(s) used for the treatment of COVID-19. Study intervention must be discontinued if prohibited medication is used.
- When a participant, for whom study intervention has been interrupted, recovers from suspected or confirmed SARS-CoV-2 infection or related disease and all adverse events (AEs) related to SARS-CoV-2 infection improve to grade ≤ 1 , the investigator should discuss with the sponsor about resuming study intervention.

COVID-19 vaccination during the study:

Local guidelines on the use of live vaccines in participants receiving PegIFN- $\alpha 2a$ should be followed, including for the second dose of Sputnik V (which contains rAd5, with a theoretical risk of replication competence). Sputnik Light, which is the first dose of Sputnik V (with rAd26) is not considered a live vaccine. See below for further guidance on the use of COVID-19 vaccines.

Locally approved COVID-19 vaccines (including those that received emergency use authorization or conditional marketing authorization) are allowed throughout the study. For participants receiving PegIFN- $\alpha 2a$ the following recommendations should be applied to accommodate COVID-19 vaccination during Treatment Period 2:

- COVID-19 vaccine and PegIFN- $\alpha 2a$ should not be administered on the same day.
- If required, PegIFN- $\alpha 2a$ injection can be delayed with 2 days. The next PegIFN- $\alpha 2a$ injection should be performed at the scheduled time.
- If required, skipping a PegIFN- $\alpha 2a$ injection may be considered after consultation with the Sponsor.
- Vaccination with Sputnik V should take above mentioned consideration about live vaccines into account.

All COVID-19 vaccination-related data (eg, COVID-19 vaccination, AEs, AE management) should be appropriately captured in the CRF and source documents. Refer to the COVID-19 vaccine and/or PegIFN- $\alpha 2a$ prescribing information for more details.

Study Visits and Assessments:

- If possible, central laboratory testing as outlined in the [Schedule of Activities](#) is to be continued. If central laboratory tests cannot be performed, the use of a local laboratory is

allowed for study evaluations. A copy of the local laboratory report should be reviewed by the investigator and filed with the source documents, along with reference ranges.

- To safely maintain participants on study intervention while site capabilities are compromised by COVID-19-related restrictions, study visits may be performed by a nurse (who received study-specific training) at the patient's home (home health nurse) until such time that on-site visits can be resumed. The following activities may be completed as required per the [Schedule of Activities](#) and as feasible:
 - Sampling, processing and shipping of laboratory samples (as described above).
 - Checking study compliance: medication diary (if available), intake of oral study intervention, storage of oral study intervention.
 - Performing electrocardiograms (ECGs).
 - If JNJ-3989 is administered at the patient's home, it will need to be done by a nurse (who received study-specific training).
 - Delivering oral study interventions, as well as PegIFN- α 2a where allowed per local regulations.^a
- Any data related to AEs, concomitant medication, vital signs, and ECGs will be reviewed and assessed by the investigator.
- In addition, participants may have tele-health visits conducted by qualified site personnel via phone or video conversation as per local regulation. Assessments may include review of AEs (including injection site reactions), concomitant medications, and study intervention accountability. Participants will also be questioned regarding general health status to fulfill any physical examination requirement.
- Procedures and timings should follow the [Schedule of Activities](#) as closely as possible. Standard AE/serious adverse event (SAE) reporting requirements apply.
- Ultrasound (and Fibroscan where applicable) should be done as close as possible to the time points specified in the [Schedule of Activities](#). However, if this is not possible due to COVID-19-related restrictions, the imaging test should be performed as soon as possible.

Informed Consent:

- Consenting and re-consenting of participants (including also remote consenting by phone or video consultation) will be performed as applicable for the measures taken and according to local guidance for informed consent applicable during the COVID-19 pandemic. The process is to be documented in the source documents.

Source Data Verification/Monitoring:

- In case on-site monitoring visits are not possible, the site monitor may contact the investigator to arrange monitoring activities remotely (in accordance with site and local requirements).

^a Delivering PegIFN- α 2a is not applicable for sites in Japan, where weekly administration of PegIFN- α 2a must be performed at the study site by the investigator or his/her designee.

Additional on-site monitoring visits may be needed in the future to catch up on source data verification.

Site Audits:

- During the COVID-19 pandemic and at the impacted sites, study site Good Clinical Practice (GCP) audits with direct impact/engagement from the investigator and study site personnel would not be conducted in order to comply with national, local, and/or organizational social distancing restrictions. Additional quality assurance activities such as remote audits or focused review of study-related documents may take place with limited impact/engagement if possible.

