JNJ-6379 is an orally administered Class N capsid assembly modulator (CAM-N) interfering with the capsid assembly and disassembly during HBV replication. JNJ-6379 binds to hepatitis B core protein (HBc) and interferes with the viral capsid assembly process, thereby preventing the polymerase-bound pgRNA encapsidation. This results in the formation of HBV capsids with normal shape but which are devoid of HBV DNA or RNA (non-functional capsids; Class N), and ultimately in the inhibition of HBV replication. In addition, JNJ-6379 also acts at an early stage of the viral life cycle by inhibiting the de novo formation of cccDNA potentially by interfering with the capsid disassembly process. JNJ-6379 was initially part of the study intervention, but has been removed as study intervention with the implementation of an urgent safety measure, as described in Protocol Amendment 3.

Select NAs and PegIFN- α 2a are approved treatments of chronic HBV infection.

For the most comprehensive nonclinical and clinical information regarding JNJ-3989 and JNJ-6379, refer to the latest version of the Investigator's Brochures (IBs) (IB JNJ-3989 2020; IB JNJ-6379 2021). For nonclinical and clinical information regarding NA and PegIFN- α 2a, refer to their respective prescribing information.

An introduction on HBV and the current treatment options is provided in Section 2 of the Master Protocol PLATFORMPAHPB2001.

As of Protocol Amendment 3, the term “study intervention” throughout the protocol, refers to JNJ-3989, NA, and PegIFN- α 2a, as defined in Section 6.1, Study Intervention(s) Administered.

The term “sponsor” used throughout this document refers to the entities listed in the Contact Information page(s), which will be provided as a separate document.

The term “participant” throughout the protocol refers to the common term “subject”.

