HLA	human leukocyte antigen
IA	interim analysis
IB	Investigator's Brochure
ICF	informed consent form
ICS	intracellular cytokine staining
IFLEP	Independent Flare Expert Panel
IFN(- α/γ)	(alpha/gamma) interferon
IgG	immunoglobulin G
IgM	immunoglobulin M
IL	interleukin
INR	International Normalized Ratio
ISA	intervention-specific appendix
ISR	injection site reaction
ITT	intent-to-treat
LLN	lower limit of normal
LLOQ	lower limit of quantification
MDSC	myeloid-derived suppressor cell
MoA	mode of action
MRI	magnetic resonance imaging
NA	nucleos(t)ide analog
NK	natural killer
NOAEL	no observed adverse effect level
PBMC	peripheral blood mononuclear cell
PD	pharmacodynamic(s)
PegIFN- α 2a	pegylated interferon alpha-2a
pgRNA	pre-genomic ribonucleic acid
PK	pharmacokinetic(s)
PoC	proof of concept
Q4W	every 4 weeks
QD	once daily
QTcF	QT interval corrected for heart rate according to Fridericia's formula
RBC	red blood cell
rcDNA	relaxed circular deoxyribonucleic acid
RNAi	ribonucleic acid interference
SAE	serious adverse event
SAP	Statistical Analysis Plan
SD	standard deviation
SDM	site-directed mutant
SE	standard error
siRNA	small interfering ribonucleic acid
$t_{1/2\text{term}}$	terminal half-life
T4	thyroxine
TAF	tenofovir alafenamide
TEAE	treatment-emergent adverse event
t_{max}	time to reach C_{max}
TND	target not detected
TNF	tumor necrosis factor
TSH	thyroid stimulating hormone
WBC	white blood cell

Definitions of Terms

ALT/AST nadir	Lowest ALT/AST value during study participation
End of study intervention (EOSI)	Time of the last administration of study intervention
HBsAg or HBeAg seroclearance	HBsAg or HBeAg negativity, respectively, based on the assay used
HBsAg or HBeAg seroconversion	HBsAg or HBeAg negativity and anti-HBs or anti-HBe antibody positivity, respectively
IC ₅₀	half maximal inhibitory concentration
Study intervention	As of Protocol Amendment 3: JNJ-73763989 (JNJ-3989), NA (either ETV, tenofovir disoproxil, or TAF), and PegIFN- α 2a (in Treatment Period 2)
Virologic breakthrough	Confirmed on-treatment HBV DNA increase by $>1 \log_{10}$ IU/mL from nadir or confirmed on-treatment HBV DNA level >200 IU/mL in participants who had HBV DNA level $<$ LLOQ of the HBV DNA assay

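### Appendix 10's COVID-19 stopping rule for prohibited medication covers the nucleos(t)ide analog (NA) by definition and has no duration threshold, so read literally it is out of line with Section 7.1

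*Protocol*

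**What the plan says.** The COVID-19 guidance in Protocol Section 10.10 (Appendix 10) has a bullet for a participant who develops SARS-CoV-2 infection. The investigator is to contact the sponsor, and continuation is left to the investigator in light of symptoms and the COVID-19 drugs used. The bullet then ends with a flat rule: "Study intervention must be discontinued if prohibited medication is used". It names no agent and sets no minimum duration.

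The term is defined elsewhere:

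- Section 2 says that, as of Amendment 3, it "throughout the protocol, refers to JNJ-3989, NA, and PegIFN"-α2a.
- The definitions in Section 10.1 (Appendix 1) read "As of Protocol Amendment 3: JNJ-73763989 (JNJ-3989), NA (either ETV, tenofovir disoproxil, or TAF"), with PegIFN-α2a added for Treatment Period 2.
- Appendix 10, on missed doses, speaks of "a scheduled administration of study intervention (JNJ-3989, NA, or PegIFN"-α2a).

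Appendix 10 also contains softening text:

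- On its general status: "This guidance does not supersede any local or government requirements or the clinical judgement of the investigator".
- On using its provisions: "Before implementing any of these emergency provisions, the sponsor should be consulted to perform a benefit-risk analysis".
- On a participant who recovers after an interruption: "the investigator should discuss with the sponsor about resuming study intervention".

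**The concern.** A site that applies the definition to the rule would stop NA in any participant given a disallowed drug for COVID-19, however short the course. Elsewhere, when the protocol stops treatment for disallowed medication, it names JNJ-3989 and PegIFN-α2a and deals with NA separately. A site would then hold two written instructions that cannot both be followed.

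What is at stake is participant safety and consistent conduct across sites. Participants enter virologically suppressed on stable NA. Section 2.3.2.2 states that stopping NA carries a risk of hepatitis B flares. Section 4.2 explains that follow-up monitoring and the re-treatment criteria were changed after a severe ALT flare following NA discontinuation in another study, in a participant with no history or evidence of cirrhosis. Appendix 10 applies when visits may be remote or delayed, which is a poor setting for an unplanned NA stop.

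**Working it through.** No arithmetic applies, so the check sets the provisions side by side and runs three cases through them.

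**Step 1: does the term include NA?** Yes, by the definitions in Section 2 and Appendix 1 and by Appendix 10's own list. Appendix 10 also speaks of oral study intervention. With JNJ-6379 removed, NA is the only oral agent left.

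**Step 2: what do the other provisions require?**

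- *Section 7.1.* Disallowed medication is a reason to stop JNJ-3989 (and PegIFN-α2a in Treatment Period 2) when two conditions hold: at least 7 days of treatment, and no intention to stop the disallowed drug. NA can go on, or can be stopped on the investigator's judgement in consultation with the sponsor.
- *Section 8.3.6.1.* If a rash needs systemic corticosteroids above 5 mg prednisolone equivalent per day (a dose that Table 3 disallows), JNJ-3989 and PegIFN-α2a stop permanently and NA is allowed to continue.
- *Section 6.6, early discontinuation before Week 24.* NA can go on or, with the sponsor, be stopped on the basis of the completion criteria.
- *Sections 4.2 and 6.6, follow-up.* A participant who does not meet the completion criteria at Week 24 stays on NA through follow-up.

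None of these makes an NA stop mandatory because a disallowed drug was used.

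**Step 3: three cases**, each with a systemic corticosteroid above the Table 3 limit given for COVID-19.

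- *Case A: treatment period, course shorter than 7 days and then ended.* The Section 7.1 criterion is not met, so nothing has to stop on that ground. Appendix 10, read literally, stops every agent, including NA.
- *Case B: treatment period, 7 days or more with no intention to stop.* Section 7.1 stops JNJ-3989 and, where applicable, PegIFN-α2a. NA remains a matter of judgement under 7.1 and 6.6. Appendix 10, read literally, also stops NA.
- *Case C: follow-up, completion criteria not met at Week 24.* NA is the only agent being taken. Sections 4.2 and 6.6 say it continues. Appendix 10 would stop it, if the sentence reaches follow-up.

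**Step 4: does the sentence reach follow-up?** The text points both ways. For: the Schedule of Activities shows NA intake under its study intervention block in the follow-up columns, Section 4.2 counts NA when it speaks of stopping all study intervention, and the corticosteroid restriction in Table 3 runs to the end of follow-up. Against: Appendix 1 defines end of study intervention as "Time of the last administration of study intervention", yet the protocol fixes that point at Week 24 even when NA goes on.

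**Result.** Cases A and B show a mismatch whichever way Step 4 is settled. In A, both the duration threshold and the treatment of NA differ. In B, only the treatment of NA differs. Case C is a sharper conflict, but it is conditional.

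**The case against.** The strongest reply is that the protocol habitually separates NA when it speaks of discontinuing study intervention. Section 7.1 carries that phrase in its title but stops JNJ-3989 and PegIFN-α2a. Section 7 sends a participant who discontinues study intervention early into follow-up, where NA may continue. End of study intervention is set at Week 24 although NA can run on. Appendix 10's parenthesis naming NA concerns missed doses, not stopping. On this view the sentence simply points to the Section 7.1 event, and investigator judgement, sponsor consultation and the provision for resuming make automatic NA withdrawal unlikely.

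Much of this stands. JNJ-3989 and PegIFN-α2a are probably all that was meant, and the practical risk is limited. It does not remove the problem. Within the same bullet the decision is first left to the investigator, and the next sentence then says it must go one way. No text tells a site that NA is exempt, and the missing 7-day threshold is a discrepancy even if NA is set aside. General concomitant-therapy rules sit in the Master Protocol, which is not among the documents reviewed.

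Two stronger readings that a reader might infer are not supported:

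- *That Appendix 10 flatly contradicts the Week 24 rule in Section 6.6.* That rule governs NA in follow-up, so the contradiction arises only if the sentence reaches follow-up, which is arguable. Before Week 24, Sections 6.6 and 7.1 are permissive, so the mismatch there is between a mandatory and a permissive instruction.
- *That the four completion criteria are otherwise the only route to stopping NA.* Section 7.1, Section 8.3.6.3 (allergic reactions) and the grade 3 and 4 rows of the rash table allow it on investigator judgement with the sponsor, and Section 6.6 has its own ALT exception. What sets Appendix 10 apart is that its stop is compulsory.

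**Conclusion.** The concern holds as a wording defect in a mandatory site instruction. Read with the protocol's own definition, the sentence makes an NA stop compulsory and drops the duration condition. That is inconsistent mainly with Section 7.1, and also with Section 8.3.6.1 and the early-discontinuation paragraph of Section 6.6. If it reaches follow-up, it is inconsistent too with the rule in 4.2 and 6.6 that NA continues when the criteria are not met. The conclusion rests on the literal reading, not on a claim about what the sponsor intended.

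Its size cannot be put in numbers. The documents give no rate of disallowed drug use for COVID-19, so no count of affected participants is offered. A reader might infer that the primary endpoint or another analysis is distorted; nothing in the documents shows that, and none is claimed. The correction is worth making because the flare risk is one the protocol itself names and the change is small.

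**What to change.** Replace the sentence in Appendix 10 with:

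> JNJ-3989 (and PegIFN-α2a in Treatment Period 2) must be discontinued if the disallowed-medication criterion in Section 7.1 is met (≥7 days of treatment with no intention to discontinue the disallowed medication); NA treatment should be continued unless it is stopped under Section 6.6 or 7.1 in consultation with the sponsor.

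This restores the 7-day condition, protects NA by default, and keeps the existing judgement route for stopping it. Naming only the Section 6.6 criteria would close the route that 7.1 leaves open, so both sections should be cited. The cost is one sentence in an appendix. No visit, assessment, analysis or sample size changes.
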